5. AMENDMENTS AND UPDATES

Amendment number	Date	Protocol section(s) changed	Summary of amendment(s)	Reason
2.0	June 27, 2023	
Study Title
 
6. Milestones
 
7. Rationale and background
 
8. Research question and Objectives
 
9.1. Study design
 
9.2. Setting
 
9.3. Variables
 
9.4. Data sources
	
Modification of the details of expression
 
Delay of protocol approval, and start of data collection
 
Modification of background explanation and addition of references
 
Modification of research question and reprioritization of objectives
 
Modification and specification of study design
 
Modification of target population and the study period
	
To represent the characteristics of the study
 
To amend protocol
 
To explain rationale and background of the study
 
To represent the characteristics of the study
 
To represent the characteristics of the study and describe the study period
 
To establish a cohort with representativeness, reliability, and efficiency
 
To analyze the data set within improved validity and reliability
 
To analyze the data set within improved validity and reliability

	9.5. Study size	Revision of estimation method of the expected number of patients	To confirm if the power of the study is sufficient
	9.6. Data management	Modification of description	To describe the data management and statistical software in detail
	9.7. Data analysis	Modification, specification, and systematization of data analysis methods	To analyze the data set within improved validity and reliability
	9.8. Quality control	Modification of description	To describe the rationale for the unnecessary of quality control and the qualifications of the research group
	9.9. Strengths and Limitations of the research methods	Modification of description	To refine description
	10.3. IRB/IEC	Modification of description	To include standard text for studies requiring IRB/IEC approval
	10.4. Ethical conduct of the study	Addition and deletion of guidance documents	To include only relevant guidance used in the study
	12. Plans for disseminating and communicating study results	Modification of description	To refine description
	13. References	Addition and deletion of references	To include all references cited in the protocol

	14. List of tables	Addition of Table 3~7 To describe variables and their operational definitions in detail, and provide evidence of estimation of the expected number of patients To show the study flow visually
	15. List of figures	Addition of Figure 2

6. MILESTONES

Milestone	Planned date
Study proposal approval	4Q 2022
Study protocol approval	2Q 2023
Start of data collection: application submission to the HIRA	3Q 2023
End of data collection: data acquisition and analysis	4Q 2023~1Q 2024
Statistical analysis report	4Q 2023~1Q 2024
Final study report	2Q 2024~3Q 2024

7. RATIONALE AND BACKGROUND

Women at menopause may experience various changes due to ovarian failure and sex hormone deficiency¹. Globally, more than half of women aged 40-64 years experience menopausal symptoms such as hot flushes, night sweating, palpitation, sexual dysfunction, depression, insomnia and osteoporosis². These symptoms can disrupt various aspects of a person's life such as their ability to sleep, concentrate, maintain a good mood, feel energetic, carry out work, and engage in leisure or social activities³. Furthermore, the burden of medical treatment for menopausal symptoms is substantial and keeps increasing, highlighting the need for effective solutions to improve the quality of life for these population⁴.

Treatment guidelines recommend MHT for vasomotor symptoms and prevention of osteoporosis in women under 60 years of age or within 10 years of menopause and without contraindications⁵. However, since the Women's Health Initiative report and the Million Women Study were published, the use of MHT has declined rapidly^{6,7}. Also, many studies have reported a potential link between MHT and increased risk of cardiovascular disease, breast cancer, and endometrial hyperplasia⁸⁻¹⁰. Therefore, many menopausal individuals also seek treatment alternatives to MHT, including selective serotonin reuptake inhibitors, serotonin-norepinephrine reuptake inhibitors, gabapentin, and clonidine¹¹, although some of them have limited effectiveness and are also associated with specific adverse effects¹².

Recently, in light of the position statement on MHT, several menopause societies concur on the necessity of individualized MHT^{13,14}. Given that there is limited evidence on the latest MHT usage pattern using the most recent data in South Korea, we aim to estimate the prevalence of MHT among menopausal women and understand treatment patterns, adherence, and persistence among patients with menopausal hormone therapy in South Korea using the nationwide claims database from 2011 to 2020.

8. RESEARCH QUESTION AND OBJECTIVES

- Research question: What are the real-world usage patterns of menopausal hormone therapy in South Korea?
- Objectives

1. To estimate the prevalence of MHT by treatment class, age group, menopausal symptoms, and the type of administration
2. To describe the baseline characteristics of patients prescribed with or without MHT
3. To examine treatment patterns, adherence, and persistence among patients with MHT

9. RESEARCH METHODS

9.1. Study design

A retrospective observational study will be conducted to examine the prevalence, treatment patterns, persistence, and adherence of commonly used MHT in South Korea, using the HIRA database from January 1, 2011 to December 31, 2020.

9.2. Setting

The study cohort will include patients aged 40-59 years who were firstly diagnosed with menopausal symptoms and initiated MHT between January 1, 2012 and December 31, 2019. Patients with menopausal symptoms will be defined as at least one inpatient or outpatient claim with any of the following diagnosis codes (Table 1), restricted to primary and secondary diagnosis. The cohort entry date will be defined as the date of first diagnosis of menopausal symptoms and the index date will be defined as the date of the first prescription for MHT.

The exclusion assessment window will be defined as the year before the index date. Patients meeting any of the following criteria will be excluded: 1) patients diagnosed with breast cancer (C50, D05), endometrial cancer (C54.1), or granulosa cell tumor (C56); 2) patients diagnosed with coronary heart disease (I20-I25, I51.6), stroke (I60-64), or VTE (I80.2, I80.3 I26); 3) Patients diagnosed with viral hepatitis (B16-B19), cirrhosis (K70.2-K70.4, K71.7, K72.0-K72.1, K72.9, K74.0-K74.6, K76.1, K76.6-K76.7, R18, I85.0, I85.9, I86.4, I86.8, I98.2-I98.3), and hepatic cancer (C22); 4) patients diagnosed with gallbladder disease (K80, K81, K82, K83, K85.1), gallbladder cancer (C23), extrahepatic bile duct cancer (C24) within 1 year prior to the index date. Baseline characteristics including demographic characteristics, and medical institution type will be assessed on cohort entry date and comorbidities, concomitant medications and proxies of health status will be assessed within 1 year prior to cohort entry date. Menopausal symptoms will be assessed within 90 days after cohort entry date. Type of administration will be assessed on index date. (Figure 1).

PFIZER CONFIDENTIAL

In the identified study cohort, we will examine treatment patterns, adherence, and persistence of MHT during the follow-up window, which will be defined from the index date (date of first prescription for MHT) to the end of the study period (December 31, 2020).

[figure not shown]
[figure not shown]

Figure 1. Study design scheme

[§] Menopausal symptoms: Vasomotor symptoms, Bone and joint symptoms

Figure 2. Study Flowchart

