 - Prevalence of each menopausal symptom including vasomotor symptoms, bone and joint symptoms, genitourinary symptoms, and psychosomatic symptoms will be calculated among patients with MHT.

- Within final study cohort, prevalence of menopausal hormone therapy by treatment class, age group, menopausal symptoms and the type of administration will be calculated for each year.
- Baseline characteristics including demographic characteristics, medical institution type, proxies of health status, comorbidities, and concomitant medications will be assessed on cohort entry date or within 365 days prior to cohort entry date. Type of administration will be assessed on index date. The baseline characteristics of patients with menopausal symptoms will be presented in frequency (proportion) for categorical variables and mean (standard deviation, SD) or median (interquartile ranges, IQR) for continuous variables.
- All outcome variables will be summarized descriptively through tables or graphical forms, including means, medians, ranges, and standard deviations of continuous variables, as well as frequency distributions of categorical variables.
- We will evaluate annual and quarterly time-series trends in the prevalence of MHT between 2012 and 2020 from 4 dimensions: 1) treatment class of MHT: ET (estrogen therapy), EPT (estrogen-progestin therapy), and tibolone. 2) age group: all, 40-44, 45-49, 50-54, and 55-59. 3) menopausal symptoms: vasomotor symptoms, bone and joint symptoms, genitourinary symptoms, and psychosomatic symptoms. 4) type of administration: systemic HT (oral), systemic HT (transdermal), and local HT (transvaginal).
- For treatment change pattern analysis, the treatment will be categorized and the proportional flows of patients switching the treatment classes will be demonstrated by Sankey diagram.
- Kaplan-Meier survival curves will be generated to calculate the time to non-persistence events including switch and discontinuation. Discontinuation will be defined as no subsequent prescriptions within 2 months of last prescription date.
- Treatment persistence is calculated by the average length of treatment of the drugs prescribed at the index date. Persistence rate at 3-, 6-, 9-, and 12-month were also calculated.
- Treatment adherence will be evaluated using medication possession ratio (MPR) calculated as the total number of days of medication supply divided by the number of days in the follow-up period.

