9.2.1. Inclusion criteria

Patients must meet all of the following inclusion criteria to be eligible for inclusion in the study:

Using the HIRA database, which covers the entire Korean population of ≥ 50 million, we will include patients who meet all the following the inclusion criteria.

1. Patients aged 40-59 years at cohort entry date.
2. Patients who had at least one inpatient or outpatient diagnosis of menopausal symptoms (detailed below) between January 1, 2012 and December 31, 2019.

Table 1. Diagnosis codes for inclusion

KCD-8* code	Description
N95.1	Menopausal and female climacteric states
N95.2	Postmenopausal atrophic vaginitis
N95.3	States associated with artificial menopause
N95.8	Other specified menopausal and perimenopausal disorders
N95.9	Menopausal and perimenopausal disorder, unspecified
M80.0	Postmenopausal osteoporosis with pathological fracture
M81.0	Postmenopausal osteoporosis
M81.99	Osteoporosis, unspecified, site unspecified; Osteopenia

PFIZER CONFIDENTIAL

M85.99	Disorder of bone density and structure, unspecified, site unspecified; Osteopenia, mild; Osteopenia, moderate; Osteopenia, severe
--------	---

*KCD-8 (Korean standard classification of disease, 8th revision): Korean version of ICD-10 (International statistical classification of diseases and related health problems, 10th revision)

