9.3.2 Outcomes

We will examine the treatment patterns of patients with MHT.

- 1) Prevalence of menopausal symptoms and use of MHT among women aged 40 – 59 years.
 - The annual prevalence of menopausal symptoms will be calculated as the number of women diagnosed with menopausal symptoms divided by the mid-year population of women aged 40 – 59 years.
 - The annual prevalence of menopausal symptoms with MHT will be calculated as the number of women diagnosed with menopausal symptoms and prescribed with MHT divided by the mid-year population of women aged 40 – 59 years.
- 2) Prevalence of each menopausal symptom among patients with MHT.
 - Menopausal symptoms will be classified into 4 categories: vasomotor symptoms, bone and joint symptoms, genitourinary symptoms, and psychosomatic symptoms. (Table 3)
 - The prevalence of each menopausal symptom among patients with MHT will be calculated as the number of patients diagnosed with each menopausal symptom divided by the number of patients prescribed for MHT.

Table 3. Menopausal symptoms

Menopausal symptoms	KCD-8 code
Vasomotor symptoms	N95.1 (Menopausal and female climacteric states) N95.3 (States associated with artificial menopause) N95.8 (Other specified menopausal and perimenopausal disorders) N95.9 (Menopausal and perimenopausal disorder, unspecified) R23.2 (Flushing) [§]
Bone and joint symptoms	M80.0 (Osteoporosis with pathological fracture) M81.0 (Postmenopausal osteoporosis) M81.99 (Osteoporosis, unspecified, site unspecified; Osteopenia)

	M85.99 (Disorder of bone density and structure, unspecified, site unspecified; Osteopenia, mild; Osteopenia, moderate; Osteopenia, severe)
Genitourinary symptoms	N94.1 (Dyspareunia) N95.0 (Postmenopausal bleeding) N95.2 (Postmenopausal atrophic vaginitis) F52.6 (Nonorganic dyspareunia)§
Psychosomatic symptoms	F32 (Depressive episode)§ F33 (Recurrent depressive disorder)§ F51 (Nonorganic sleep disorders)§ G47 (Sleep disorders)§

§R23.2, F32, F33, F51, F52.6, G47 are considered as diagnosis codes for menopausal symptoms only when they are obtained by obstetrics and gynecology specialists. (DGSBJT_CD:10)

- 3) Secular trend in the prevalence of MHT by treatment class, age group, menopausal symptoms, and the type of administration
 - We will examine annual and quarterly time-series trends in the prevalence of MHT between January 1, 2012, and December 31, 2020.

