 - First, we will examine trends by 3 classes of MHT: ET (estrogen therapy), EPT (estrogen-progestin therapy) and tibolone. The time-series trend will be presented as the proportion of each class of MHT quarterly, calculated as the number of patients receiving each class of MHT divided by the total number of patients prescribed with MHT.
 - Second, we will examine trends by age group: all, 40-44, 45-49, 50-54, and 55-59. The time-series trend will be presented as the proportion of MHT use by each age group, calculated as the number of patients in each age group divided by the total number of patients prescribed with MHT.
 - Third, we will examine trends by menopausal symptoms: vasomotor symptoms, bone and joint symptoms, genitourinary symptoms, and psychosomatic symptoms. The time-series trend will be presented as the proportion of MHT use by each menopausal symptom, calculated as the

number of patients with each menopausal symptom divided by the total number of patients prescribed with MHT.

- Fourth, we will examine trends by the type of administration: systemic HT (oral), systemic HT (transdermal) and local HT (transvaginal). The type of administration of MHT will be classified as follows (Table 4). The time-series trend will be presented as the proportion of MHT use by each type of administration, calculated as the number of patients with MHT by each type of administration divided by the total number of patients prescribed with MHT.

Table 4. Type of administrations

Type of administrations	Ingredient code
Systemic HT (oral)	All ingredient codes except those for systemic HT (transdermal) and local HT (transvaginal)
Systemic HT (transdermal)	154902CCM 154904CPC 154905CPC 154906CPC 154907CSI 154908CCM 154908COM 154930CCM 154931CCM 154932CCM 154601CPC 154602CPC 154603CPC 154604CPC 154605CPC 154606CPC 335900CPC 336000CPC

Local HT (transvaginal)	155303CCM 155402CCM 155430CCM 155201CCM 155202CSP 507700CTB 336200CTB 155502CCM 219001CCS 219001CCM 219030CCM 336100CTB
-------------------------	--

4) Treatment regimens change of MHT across time

- We will depict treatment switch and discontinuation patterns across time by measuring the number of different treatments, including ET, EPT and tibolone, at time points of 3, 6, 9, and 12 months from the index date. Switching and discontinuation of MHT across time will be presented with a Sankey diagram.

5) Time to switch and discontinuation of MHT

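### The 2012-2020 trends in MHT mix are placed in a cohort that closes to entry at the end of 2019, so shares by class, route, symptom and age can drift, mainly in the first years and in 2020, without any change in prescribing

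*Combined protocol and SAP*

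**What the plan says.** Section 9.2 describes the cohort as "patients aged 40-59 years who were firstly diagnosed with menopausal symptoms and initiated MHT between January 1, 2012 and December 31, 2019". The listed criteria in 9.2.1 are looser. They date only the diagnosis, "Patients who had at least one inpatient or outpatient diagnosis of menopausal symptoms (detailed below) between January 1, 2012 and December 31, 2019", and set age only at entry, "Patients aged 40-59 years at cohort entry date".

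The data analysis part of the abstract gives the population for the four-way breakdown, year by year: "Within final study cohort, prevalence of menopausal hormone therapy by treatment class, age group, menopausal symptoms and the type of administration". Section 9.3.2, Outcome 3, sets the calendar span: "We will examine annual and quarterly time-series trends in the prevalence of MHT between January 1, 2012, and December 31, 2020". The measure is a share among users. For class it is "calculated as the number of patients receiving each class of MHT divided by the total number of patients prescribed with MHT", and the age, symptom and route trends have the same denominator (9.3.2 and 9.7).

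Outcome 1 is a different quantity. It "will be calculated as the number of women diagnosed with menopausal symptoms and prescribed with MHT divided by the mid-year population" of women aged 40-59, and the text does not tie it to the cohort.

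The claims cover January 2011 to December 2020 (9.4). No 2011 washout is stated for a first diagnosis. Neither 9.7 nor the limitations in 9.9 mention a burn-in period, an adjustment for time since start, or the closed entry in 2020.

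**The concern.** Entry lasts eight years and the trend series nine. In a cohort filled and closed this way, calendar time is tied to time since MHT start. Early periods hold mostly recent starters, later ones add long-term users, and 2020 holds almost only women who have stayed on treatment. A class, route or symptom group with shorter use then shrinks as a share of users even if prescribing at initiation never changes.

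Outcome 3 is the time-trend part of the first-listed objective. A reader of the published series would take a step in the 2020 mix as a change in practice.

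**Working it through.** **Plan's own figures.** The plan gives no persistence, class share or expected trend, so there is nothing to reproduce on this point. The eight yearly totals in Table 7 do add to the stated 4,293,747, but that number plays no part here.

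**Inputs from the plan.** Entry runs from 1 January 2012 to 31 December 2019 (9.2). The series runs from 2012 to 2020, and the measure is a share among users (9.3.2).

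**Assumptions (not in the plan).** Starts are constant at 1 unit per class per year. Two classes each make up half of starts. Time on treatment is exponential. There are no prevalent users at entry, no restarts and no switching. There is therefore no true trend.

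**Formula.** Let p be 12-month persistence, λ = −ln p per year, and a the years from 1 January 2012 to the start of the calendar year. Users in that year are N = s + (1 − p^a)/λ, with s = 1 for 2012-2019 and s = 0 for 2020, when 9.2 allows no starts.

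**20% versus 50%** (λ = 1.609 and 0.693):

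| Year | a | Shorter use | Longer use | Share of shorter use |
|---|---|---|---|---|
| 2012 | 0 | 1.000 | 1.000 | 50.0% |
| 2014 | 2 | 1 + 0.96/1.609 = 1.597 | 1 + 0.75/0.693 = 2.082 | 43.4% |
| 2019 | 7 | 1.621 | 2.431 | 40.0% |
| 2020 | 8 | 0.621 | 1.437 | 30.2% |

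An open population under the same assumptions has N = 1 + 1/λ, or 1.621 and 2.443. That is a flat 39.9% every year.

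**30% versus 40%** (λ = 1.204 and 0.916): the shares are 50.0%, 47.8%, 46.7% and 43.2%; the open population is flat at 46.7%.

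**Equal persistence:** both classes have the same N, so the share is 50% throughout.

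**Quarterly.** The same model by quarter gives 50.0% in Q1 2012, 34.1% in Q4 2019 and 17.9% in Q4 2020 for 20% versus 50%. For 30% versus 40% it gives 50.0%, 44.6% and 38.0%.

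**Second check, three classes.** With equal starts and assumed mean durations of 6, 12 and 18 months, the longest-use class in the closed cohort has 33.3% (2012), 38.7% (2014), 41.7% (2019) and 50.6% (2020). The open population is flat at 41.8%. Allowing starts through December 2020 brings the 2020 figure back to 41.8%. With longer assumed durations (12, 24 and 48 months) the build-up lasts longer: 33.3%, 38.6%, 46.8% and 54.3%, against an open 50.2%.

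**Age.** Because age is limited only at entry, a woman entering at 59 in 2012 is about 67 in 2020, outside every planned band. The plan does not say whether the age trend uses entry age or current age.

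**The case against.** The strongest reply is that only one sentence in the abstract ties these trends to the cohort. Sections 9.3.2 and 9.7 divide by all patients prescribed MHT, and 9.2 names the cohort only for treatment patterns, adherence and persistence. The body could therefore be read as already separating the two. That stands as an ambiguity but does not remove the point. No body section names another population for Outcome 3, and the symptom dimension is assessed in the 90 days after cohort entry, so it needs an entry date.

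Four limits on the claim do stand.

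- Shares move by class, route or symptom only if persistence differs by that factor, and the documents give no persistence figures.
- The quarterly numbers are the extreme case. Section 9.7 spells out quarterly proportions only for class, and annual shares move less.
- The early drift is an upper figure. Without a washout, prevalent patients could enter at their first 2012 claim and soften it.
- That 2020 has no new starters follows from 9.2 alone. Under 9.2.1 a woman diagnosed by the end of 2019 could start in 2020. If such starts ran at half the usual rate (assumed), the 2020 share at 20% versus 50% would be (0.5 + 0.621)/(1 + 0.621 + 1.437) = 36.7%, not 30.2%.

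A reader might also infer that the plan will show total MHT use collapsing in 2020. In the model, cohort users do fall from 4.05 to 2.06 units, or 49%, between 2019 and 2020. But Outcome 3 plans shares, not counts, and overall use is Outcome 1, which uses the mid-year population. The documents do not support that stronger reading.

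**Conclusion.** The point holds for Outcome 3 and should be fixed. Followed as written, the plan computes the 2012-2020 mix in a population that no newly diagnosed woman can join in 2020 and that may still be filling in the first years. The direction of the artefact is certain wherever persistence differs between groups; its size is not. In the two-class illustration the step from 2019 to 2020 is 9.8 points (40.0% to 30.2%) at 20% versus 50% and 3.5 points (46.7% to 43.2%) at 30% versus 40%. The change from 2012 to 2014 is 6.6 and 2.2 points. These figures rest on constant starts, equal class shares at start, exponential time on treatment, no prevalent users and no 2020 starts. The age trend has a further problem of its own, since age is fixed only at entry. The point does not reach Outcome 1, nor Outcomes 4-6, for which an initiator cohort is suitable.

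**What to change.** In 9.2, 9.3.2 (Outcome 3), 9.7 and the abstract, define Outcome 3 as repeated cross-sections. For each quarter or year from 2012 to 2020, count all women aged 40-59 in that period who have an MHT prescription in it and a Table 1 diagnosis within a fixed look-back, including diagnoses made in 2020. The look-back must be the same for every period, for example the 12 months up to the prescription, which the 2011 data allow. A rule of any earlier diagnosis would create a new build-up, because claims begin in January 2011. State how the exclusions apply, since they are now anchored to the index date, and state that age is current age. Keep the 2012-2019 initiator cohort for Outcomes 4-6.

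Alternatively, report the mix among new starters by period of start and end the series at Q4 2019.

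Either way, reconcile 9.2, 9.2.1 and the abstract on whether MHT must start by the end of 2019, and state whether 2011 serves as a washout.

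The cost is mainly wording and a second population to program. The planned claims years already cover 2011-2020. The documents do not show how the data request is specified; if it selects on diagnosis date, that window must run through 2020. The small downside is that trend and persistence outcomes will describe different populations, which must be labelled.

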9.2.2. Exclusion criteria

1. Patients diagnosed with breast cancer (C50, D05), endometrial cancer (C54.1), and granulosa cell tumor (C56) within 1 year prior to the index date.
2. Patients diagnosed with coronary heart disease (I20-I25, I51.6), stroke (I60-64), and VTE (I80.2, I80.3 I26) within 1 year prior to the index date.
3. Patients diagnosed with viral hepatitis (B16-B19), cirrhosis (K70.2-K70.4, K71.7, K72.0-K72.1, K72.9, K74.0-K74.6, K76.1, K76.6-K76.7, R18, I85.0, I85.9, I86.4, I86.8, I98.2-I98.3), and hepatic cancer (C22) within 1 year prior to the index date.
4. Patients diagnosed with gallbladder disease (K80, K81, K82, K83, K85.1), gallbladder cancer (C23), extrahepatic bile duct cancer (C24) within 1 year prior to the index date.

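### Objective 2 covers women with and without MHT, but the text restricts the cohort to initiators in one place and ties all four exclusions to a first-MHT date that untreated women do not have

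*Combined protocol and SAP*

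**What the plan says.** Section 8 gives Objective 2 as: "To describe the baseline characteristics of patients prescribed with or without MHT". The rest of the plan describes the population for this objective in different ways.

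- **Section 9.2** builds the cohort from women aged 40-59 "who were firstly diagnosed with menopausal symptoms and initiated MHT between January 1, 2012 and December 31, 2019". Cohort entry is the first diagnosis of menopausal symptoms, and "the index date will be defined as the date of the first prescription for MHT".
- **Section 9.2.1** sets only an age range and a diagnosis: "Patients who had at least one inpatient or outpatient diagnosis of menopausal symptoms" in 2012-2019. It does not mention MHT. The abstract's inclusion criteria do the same.
- **Exclusions.** Section 9.2 says: "The exclusion assessment window will be defined as the year before the index date". Each of the four criteria in section 9.2.2 repeats that anchor; the first ends "granulosa cell tumor (C56) within 1 year prior to the index date".
- **Baseline.** Sections 9.3.3 and 9.7 speak of patients with MHT only, whereas the abstract speaks of patients with menopausal symptoms. Apart from type of administration, the baseline variables are taken at, or in the year before, cohort entry.
- **Section 9.5** calls diagnosed women the study cohort, but says that the number being estimated is that of patients with MHT.

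**The concern.** Describing two groups requires a rule for who is in each and the same screening for both. The text supplies neither for women without MHT. If the analyst follows section 9.2, there are no such women to describe. If the analyst follows section 9.2.1, untreated women enter, but the exclusions refer to a date they do not have. Users would be screened for the listed cancers, coronary heart disease, stroke, VTE, and liver and gallbladder disease; non-users would not be, unless the analyst invents a date.

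The two groups could then show different hospitalisation counts, visit counts or comorbidity scores purely because of the exclusion rule. Two analysts could also produce different tables from the same text. That matters here because section 9.8 relies on two researchers working independently and cross-checking.

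**Working it through.** **The plan's own size figure.** The yearly totals in Table 7 give 591,775 + 574,602 + 543,226 + 526,981 + 521,527 + 518,129 + 507,824 + 509,683 = 4,293,747, as section 9.5 states. The four age rows also add up to each yearly total. The figure is not split by MHT, so it cannot show how many women are affected.

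**The two cohort texts, followed literally.**

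1. *Section 9.2.* Entry requires starting MHT. Every member is a user, so the group without MHT has 0 women and Objective 2 cannot be met.
2. *Section 9.2.1.* Entry requires age and a diagnosis. Untreated women are included. The exclusion test asks for a listed diagnosis in the year ending at the index date. With no MHT prescription there is no index date, so the test cannot be evaluated. This applies to 4 of the 4 criteria.

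**What would show in the table under case 2.** Table 5 defines comorbid cancer as C00-C97 without C22, C23, C24, C50, C54.1 and C56. These are the C-coded cancers on the exclusion list, which suggests a table designed for a screened population. In an unscreened group the cancer row would not display those cancers, while any hospitalisations, visits or comorbidity score that go with them would remain. The documents give no frequency for any excluded diagnosis, so the resulting difference cannot be calculated.

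**Is there a date that both groups share?** Cohort entry is defined for every diagnosed woman and already anchors most of the baseline variables. Data start on 1 January 2011 and the earliest entry is 1 January 2012, so the shortest available look-back is 365 days. A one-year exclusion window before cohort entry is therefore covered for everyone.

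**Does the class depend on when a woman enters?** The text gives no period over which MHT is counted. Suppose, as an assumption, that any MHT up to the end of data (31 December 2020) counts:

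- entry on 31 December 2019: 366 days of observation after entry;
- entry on 1 January 2012: 3,287 days.

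Under that assumption the class depends on entry year. Two further cases are unplaced: a woman whose first MHT precedes her first recorded diagnosis, and a woman whose first MHT falls in 2020, who is outside section 9.2's initiation period yet not untreated.

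**Are untreated women already needed?** Yes. Outcome 1 in section 9.3.2 uses "the number of women diagnosed with menopausal symptoms divided by the mid-year population" and, separately, "the number of women diagnosed with menopausal symptoms and prescribed with MHT divided by the mid-year population". The first count includes diagnosed women with no MHT.

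**The case against.** The best defence is that the two cohort texts are nested steps: first all diagnosed women, dated by cohort entry, then the initiators among them, dated by the index date. The two separate dates and the anchoring of baseline to cohort entry fit this reading. Figure 2, a flowchart added in version 2.0, may show the branch and the exclusion step, and it is not available here. The objective is descriptive, no between-group test is planned, and the objection is right that this limits the harm.

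These points have force but do not remove the problem. A nested reading leaves the exclusion date for untreated women undefined, and sections 9.3.3 and 9.7 still omit those women. Even if the figure resolves the matter, the text of 9.2, 9.2.1, 9.3.3 and 9.7 would need to be aligned with it.

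The objection also rightly limits what can be said about intent. A reader might infer from the abstract's plan for MHT prevalence within the final study cohort that this cohort must be all diagnosed women. The documents do not establish that: sections 9.3.2 and 9.7 put the proportions by class, age, symptom and route over patients prescribed MHT, which fits a cohort of users equally well. Outcome 1 is a population rate and does not define the study cohort either.

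**Conclusion.** The point stands for the text. A stated rule (exclusions in the year before first MHT) and a stated restriction (initiators only) defeat a stated objective (describing women with and without MHT). As written, the second group is either empty or screened differently from the first. The reach is Objective 2 only: Objective 3 concerns initiators, who do have an index date. Most baseline variables are unaffected in their timing; the gap is in group membership and exclusions.

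The size of the effect cannot be derived. A reader might take 3,287 / 366, about 9.0, as a measure of distortion. It is not: it compares two extreme entry dates under a counting rule that the plan does not state, and no distribution of entry dates among women with or without MHT is given. Nor does section 9.2's initiation limit yield a range for classifying untreated women, because under that wording there are none. A reader might also conclude that the plan contains no classification rule anywhere; with Figures 1 and 2 not shown, only the text can be said to lack one.

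**What to change.** For Objective 2:

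- State that the parent cohort is all women meeting section 9.2.1.
- Apply the four exclusions to both groups in the year before cohort entry.
- Report baseline for both groups in sections 9.3.3 and 9.7.
- Align sections 9.2, 9.2.2 and 9.5 and the abstract, and check Figures 1 and 2 against them.
- State how a woman is classed as with or without MHT, including MHT before the first diagnosis and first MHT in 2020.

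Keep the index-date exclusions for the Objective 3 initiator cohort.

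The classification window is the sponsor's choice. A fixed window of up to 366 days after cohort entry lies inside the data for every woman, but it has drawbacks. Later starters would be without MHT in Objective 2 and initiators in Objective 3, some 2020 starts would count for late entrants, and MHT before the first diagnosis would need its own rule.

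The cost is protocol wording and one more baseline column. Outcome 1 already needs all diagnosed women, so the data request needs at most a check that person-level records for untreated women are included. The main downside is that the user group and the exclusion counts will differ between Objectives 2 and 3, by an amount that the documents do not allow to be stated. For a woman who enters on 1 January 2012 and starts MHT on 31 December 2019, the two exclusion dates are 2,921 days apart. The report should explain the difference.
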